 6.5 Length of Study 16

7.0 Data Management 16

8.0 Confidentiality and Privacy 16

9.0 Data Safety and Monitoring..... 16

10.0 WFUHS IRB AE Reporting Requirements..... 17

[figure not shown]
11.0 Reporting of Unanticipated Problems, Adverse Events or Deviations 17

Pilot Study: Metabolic and microbial profiling of lung cancer
Wake Forest Baptist Comprehensive Cancer Center (WFBCCC)
WFBCCC # 03219

Appendix A – Subject Eligibility Checklist 19
Appendix B – Protocol Registration Form 20

Pilot Study: Metabolic and microbial profiling of lung cancer
Wake Forest Baptist Comprehensive Cancer Center (WFBCCC)
WFBCCC # 03219

SCHEMA

Primary Outcomes:
Assess feasibility of adding these non-invasive collections to pre- and post-surgery

Secondary Outcomes:
Assess changes in metabolites and microbial populations between lung cancer patients' biosamples pre- and post-surgery
Identification of lung cancer stage specific signatures
Identify signatures which associate with pulmonary function

1.0 Introduction and Background

Lung cancer (LC) is the second most common type of cancer and leading cause of cancer-related deaths in the United States (1). It is estimated that there will be over 120,000 new cases in 2018 (1). Early detection leads to earlier treatment, and early LC stage detection has clear benefit in survival rates(2). Clinical tools for diagnostic screening of LC are limited, but efforts have been made to develop molecular techniques to identify LC during bronchoscopy procedures (3). The National Lung Screening Trial screened patients at high-risk of LC by computed tomography (CT) scans (4). Mortality rates were reduced through the screening, but a number of challenges to CT screening were noted. For example, one in four patients showed incidental abnormalities in the lung potentially not representing LC, and further invasive tests including biopsies and/or surgery were required to rule out cancer(4). Additionally, the uncertainty surrounding incidental findings is suspected to lead to further patient stress, which may further impact the patient's health.

It is apparent that complex diseases, like cancer, require powerful and sensitive technologies to uncover underlying mechanisms of the disease and even to detect the presence of the disease. A metabolomics approach is able to obtain a snapshot of biological and molecular mechanisms underlying a disease process by capturing metabolic profiles that are indicative of cellular metabolism. Current profiling technology results in the identification of hundreds to thousands of metabolites, which can be used as an unbiased analysis of biochemical pathways and potentially target biological dysfunction(5) (6) (7). A number of studies have utilized metabolomics approaches to profile LC (8). Many of these studies focused on tumor versus non-tumor tissue or serum in cancer patients versus healthy controls. We seek to assess metabolic signatures in samples from patients before and after surgical removal of their tumor.

Recent studies have also focused on the link between cancer and the human microbiota, with special interest in determining how the oral microbiota contributes to the pathogenesis of various cancer types, including LC(9). It is well-established that the lungs are not sterile, and scientists have recently demonstrated that the lung microbiome is very similar to the oral microbiome(10); (11); (12). Furthermore, periodontal disease is associated with LC risk(13); (14), suggesting an association between the oral microbiome and LC risk, but further studies are needed to determine how oral microbial variations contribute to LC(9). The most informative approach to assessing the human microbiota is through shotgun metagenomic sequencing, which allows the characterization of microorganisms down to the species or even strain level and provides information on the putative function of the microbiota. Collecting saliva before and after surgical resection offers a noninvasive approach for studying the role oral microbiota play in LC, which has not previously been done.

Utilizing these unbiased approaches will be pivotal to understanding the molecular dysregulation in LC and will potentially lead to the discovery of novel signatures within non-invasive biosamples that can be used as a diagnostic tool for identifying and characterizing LC. Our long-term goal is to translate findings from this study into diagnostics for the clinic, giving clinicians robust information to identify at-risk patients prior to the observation of symptoms. The need for a non-invasive, low-risk, highly-specific diagnostic tool for LC is still evident. By profiling patients prior to and post-surgical resection, we will identify potential molecular markers that may be indicative of LC.

2.0 Objectives

Pilot Study: Metabolic and microbial profiling of lung cancer
Wake Forest Baptist Comprehensive Cancer Center (WFBCCC)
WFBCCC # 03219

This pilot study will establish non-invasive sample collections, including breath, saliva, blood and urine pre-surgery and at the patient's one-month post-surgery follow-up visit. Patients with suspected non-small cell lung cancer (NSCLC) stage I-III will be recruited from Co-I [name]'s clinic.

2.1 Primary Objective

2.1.1 To evaluate the feasibility of adding non-invasive sample collections in the pre-surgical setting and at the post-surgery follow-up visit.

2.2 Secondary Objective

2.2.1 To identify and assess metabolic and microbial signatures collected at pre- and post-surgery and determine which are indicative of LC.

2.2.2 To identify signatures which are associated with LC stage

2.2.3 To identify signatures which are impacted by patient's pulmonary function status

3.0 Study Population

3.1 Inclusion Criteria

3.1.1 Male and female patients age ≥ 18 years, of all racial and ethnic origins, with suspected NSCLC stages I, II, and III, as evident through radiographic evidence and felt acceptable to undergo surgical resection.

3.1.2 Patients who have the ability to understand and the willingness to sign a written consent form.

3.2 Exclusion Criteria

3.2.1 Patients who are have taken antibiotics within two weeks.

3.2.2 Patients who are on continuous supplemental oxygen.

3.2.3 Patients currently undergoing active treatment for other malignancies.

3.2.4 Subjects who are unable or unwilling to provide consent.

3.3 Inclusion of Women and minorities

3.3.1 Women and men of all races and ethnicity who meet the above-described eligibility criteria are eligible for this trial.

3.3.2 The study consent form will also be provided in Spanish for Spanish-speaking participants. Based on WFBCCC population estimates, approximately 51% of participants to will be women. Translating this to our sample size estimate of 90, we plan to enroll 45 women and 45 men. Similarly, we expect approximately 6.6% of study participants to be Hispanic/Latino (N=6), 13.3% Black or African

Pilot Study: Metabolic and microbial profiling of lung cancer
Wake Forest Baptist Comprehensive Cancer Center (WFBCCC)
WFBCCC # 03219

American (N=12), 0.48% American Indian/Alaska Native (N=1), and 1.8% Asian (N=1).

4.0 Methods

4.1 Registration Procedures

All patients entered into any WFBCCC trial, whether treatment, companion, or cancer control trial, **must** be linked with a study protocol in EPIC within 24 hours of Informed Consent. Patients **must** be registered prior to the initiation of the study.

You must perform the following steps in order to ensure prompt registration of your patient:

- 1.0 Complete the Eligibility Checklist (Appendix A).
- 2.0 Complete the Protocol Registration Form (Appendix B).
- 3.0 Alert the Cancer Center registrar by phone, *and then* send the signed Informed Consent Form, Eligibility Checklist and Protocol Registration Form to the registrar, either by fax or e-mail.

*Protocol Registration is open from 8:30 AM - 4:00 PM, Monday-Friday.

- 4.0 Fax/e-mail ALL eligibility source documents with registration. Patients **will not** be registered without all required supporting documents.

Note: If labs were performed at an outside institution, provide a printout of the results. Ensure that the most recent lab values are sent.

To complete the registration process, the Registrar will:

- assign a patient study number
- register the patient on the study

4.2 Experimental or Data Collection Methods

4.2.1 Clinical data collection:

All patients will be recruited within the Wake Forest Medical Center.

Medical history will be obtained from the patients charts to identify demographics (age, race, ethnicity, zip code), oncologic history (date of diagnosis and cancer type), and medical history of disease. Pulmonary function tests (PFTs) will be performed by Wake Forest Baptist Health Pulmonary Function Lab as a standard of care for pre-surgical assessment. PFTs will be accepted from other certified laboratories within six months of their appointment. Pulmonary function is

Pilot Study: Metabolic and microbial profiling of lung cancer
Wake Forest Baptist Comprehensive Cancer Center (WFBCCC)
WFBCCC # 03219

defined by undergoing standard pulmonary function studies per American Thoracic Society recommendations. The collection of these pulmonary function studies is often done as part of the pre-surgical assessment collected by a cardiothoracic surgical team. Also, the collection of pulmonary functions studies can help with the classification and treatment of underlying obstructive lung disease that can be crucial to post-operative management.

At pre- and post- surgery, the research nurse will obtain current medications, food/ingestion survey and tobacco use information. This information will be necessary to identify any exogenous factors confounding both metabolic and microbial signatures. Following surgery, information from the patient's final pathology report will be obtained to provide information on the tumor site location, characteristics of the cancer removed, and stage of the cancer.

4.2.2 Non-invasive sample collections:

Pre-surgery follow-up collection: During the patient's surgery consultation meeting with [name], Upon entering the are the patient will be given a receptacle for collection of a urine specimen. Given that blood collection may be seen as invasive to the patient, the patient will be prompted for a blood sample. If the patient agrees, the research nurse will collect 1 redtop vacutainer serum tube and 1 purple top blood tube from the patient. We will then initiate the saliva and exhaled breath volatiles (EBV) and

exhaled breath condensate (EBC) collection. For the saliva collection, patients will be given a saliva collection receptacle. This receptacle (SalivaBio – Passive Drool) allow for sterile transfer of saliva from the patient's mouth into collection tubes. For exhaled breath collection, we will utilize the ReCIVA (Figure 1, Owlstone medical), breath collection device. The device will be attached to the in-house medical air supply (yellow) with airflow set to 40L/min per the company's recommendation (Figure 2). One-time use masks will be placed over the patient's mouth and nose. The patient will be allowed to breathe normally to acclimate themselves to the mask and airflow. The patient will be allowed to hold the device, if desired, and a head strap will be placed around their head for additional support and comfort. Once the patient is acclimated (<1 min), they will be prompted to start the collection. Pre-loaded collection parameters will be set with the device software to simultaneously collect four tubes of exhaled breath from patient's expired breath. Each metal tube (pictured in Figure 1) is packed with material to bind volatile chemicals. Once collection begins, the system will learn the breathing pattern of the patient (25 sec) and will adjust the collection pumps accordingly. Breath collection will take between 5-7 min, depending on the patient's breathing rate and total collection volume. This study will collection 500 mL of exhaled breath on each of the four tubes. All exhaled breath samples will be stored at 4°C until analysis. For exhaled breath condensate, we

Figure 1: ReCIVA breath collection device

[figure not shown]

Figure 2: Clinic breath gas collection setup

Figure 3: R-tube breath collection device

Pilot Study: Metabolic and microbial profiling of lung cancer
Wake Forest Baptist Comprehensive Cancer Center (WFBCCC)
WFBCCC # 03219

will utilize the R-tube collection device (Respiratory Research Inc.) (Figure 3). The R-tube is a one-time use apparatus that utilizes a metal cooling sleeve, placed over the plastic tube, to cool the patient's breath, creating condensation build up within the device. The patient will breathe through the mouth piece for 10 min. Following the collection, a metal plunger will be used to consolidate the condensate within the collection tube and the EBC sample can be transferred to a fresh sterile tube. The saliva, urine and blood tube will be transported to the research lab at room temperature and processed within two hours. All biofluids will be aliquoted, frozen and stored at -80° C until analysis.

Surgical tumor removal: In addition to our non-invasive collections, as part of the Advanced Tumor Bank protocol, the tumor tissue will be collected and banked. We will obtain tumor tissue samples from the Advanced Tumor Bank following processing.

Post-surgery follow-up collection: 24-48 hours prior to their 4-week in-clinic follow-up appointment, patients will be called to remind them for their 4-week follow-up, and follow-up collections will be performed in [name] clinic, 4th floor of the Cancer Center. Upon entering the clinic, the patient will be taken the research nurse visit room. The research nurse will obtain current medications and tobacco use information. The patient will be prompted for a urine sample. If the patient again agrees to a blood sample, the research nurse will collect 1 redtop vacutainer serum tube and 1 purpletop vacutainer EDTA tube from the patient. We will initiate the saliva and exhaled breath collection as described above. Following all of the collections, the patient will be given their incentives for participating in the study.

All samples collected from this study will be banked and will have the potential to be used for future scientific experimentation, which may include additional genetic, proteomic, and metabolomic analyses not described in the data collection section below.

Research Data Collection:

Data generation: Unbiased metabolomics analysis of bio-volatiles and biofluids has the potential to identify 100-1000's of metabolites in any single sample. Our group has successfully assessed bio-volatiles and biofluids by unbiased metabolomics (15) (16) Although there is no single method that allows for the complete analysis of the metabolite, utilizing multiple modes of sample preparation and analysis will potentially identify a number of classes of compounds relevant to this study. The bio-volatile that will potentially be identified are various hydrocarbons, aldehydes, ketones, and alcohols. Through our biofluids analysis we will potentially identify amino acids, sugars, nucleotides, citric acid cycle intermediates through our GCMS analysis while our LCMS analysis will identify a wide range of lipids (e.g. ceramides, sphingomyelins, cholesteryl esters, oxysterols, lyso- and phospholipids, mono-, di- and triacylglycerols, galactosyl- and glucuronylipids, bile acids, steroids, eicosanoids/oxylipins, very short chain fatty acids).

Metagenomics assessment of the microbiome will identify populations of microbes that are present in patients at the time of collections. We will map sequencing reads to a reference database consisting of complete genomes for prokaryotes (bacteria and archaea), eukaryotes (fungi and protozoa) and viruses to identify changes in these populations down to the species or strain level. We will also identify potentially active functional profiles of the microbiota identified in the samples. We will perform a de novo assembly of the reads to identify protein coding regions, and the coding regions will subsequently be annotated with Pfam domains. The abundance of functional categories will then be estimated to build a functional profile for each sample

Pilot Study: Metabolic and microbial profiling of lung cancer
Wake Forest Baptist Comprehensive Cancer Center (WFBCCC)
WFBCCC # 03219

Breath metabolomics analysis: Exhaled breath samples will be analyzed using a Markes thermal desorber, TD100-xr, to inject breath samples onto an Agilent two-dimensional GC system 7890B in tandem with LECO's Pegasus 4D Time-of-Flight instrument system (TD-GCxGC-TOFMS). The collected spectra will be processed using LECO's ChromaTOF version 4.72 software. Initial data processing includes peak deconvolution, 1st and 2nd dimension retention time recordings, signal to noise ratio calculation, unique mass detection, peak area determination, and compound identification based on the spectral pattern similarity match against established mass spectral reference libraries (NIST14, 2014 National Institute of Standard Technology, NIH, USA). Identified spectral matches will be aligned using R-program R2DGC (17) to determine common metabolites in patients prior to and after surgery. MetaboAnalyst 4.0 will be employed to normalize and transform the data for univariate and multivariate statistical analysis (18). Additional statistical analysis may be performed using Graphpad Prism 8 (Graphpad Software, Inc)

Biofluid and tissue metabolomic analysis: Saliva, serum, urine and tissue aliquots will be prepared for analysis by standard processing according to published methodology(5); (19). Two platforms of unbiased metabolomics analysis will be completed using both a Q Exactive GC system and a Q Exactive LC system. Utilizing two chromatographic methodologies will maximize our metabolite identification coverage. The collected spectra will be processed using Thermo Scientific™ TraceFinder™ 4.1 software. The initial data processing will include baseline correction, peak deconvolution, retention index, signal to noise ratio calculation, unique mass detection, peak area determination, and compound identification based on the spectral pattern similarity match against established mass spectral reference libraries (NIST14, National Institute of Standard Technology, NIH and a high-resolution mass spectral library from TraceFinder™ software). Identified spectral matches will be identified for pre- and post-surgery following metabolomics standards initiative (MSI) guidelines for metabolite identification (Level 2), with a match score requirement of equal to or greater than 80%. Aligned metabolomic data analysis software, MetaboAnalyst 4.0, will be employed to normalize and transform the data for univariate and multivariate statistical analysis (18). Additional statistical analysis may be performed using Graphpad Prism 8 (Graphpad Software, Inc)

Biofluid and tissue microbiome analysis: DNA will be extracted from each blood, saliva and lung tumor tissue sample using the QIAamp® UCP Pathogen Mini Kit (Qiagen) with extended homogenization of the tissue samples using the Mini-Beadbeater-96 cell disrupter (Biospec Products). The quantity and quality of the DNA extracts will be determined using a DeNovix DS-11 FX+ Spectrophotometer/Fluorometer and Agilent 4200 TapeStation, respectively. The DNA will then be prepared for shotgun metagenomic sequencing using the Nextera® DNA Flex Library Preparation Kit (Illumina). DNA libraries will be normalized and quantified prior to pooling to ensure equal library representation. Pooled DNA libraries will then be sequenced using the Illumina NovaSeq 6000 S1 Reagent Kit and sequencer, generating 2 x 150 bp paired-end reads. Raw sequence reads (FASTQ files) will be imported into the Microbial Genomics Pro Suite within the CLC Genomics Workbench (version 11.0.1; <https://www.qiagenbioinformatics.com>) for QC, adapter trimming, and analysis. High-quality ($\geq Q30$) reads for each sample will be aligned to those in a blank extraction sample (negative control) that will be processed from DNA extraction through library preparation to identify and remove contaminating sequences. The filtered reads will then be aligned to a reference database consisting of complete genomes in the RefSeq database for prokaryotes (bacteria and archaea), eukaryotes (fungi and protozoa) and viruses for taxonomic profiling. The filtered reads will also be assembled into contigs *de novo*, and MetaGeneMark (20) will be used to identify protein-coding regions within the reads to predict functional diversity of the microbiota identified in the samples. The coding regions will be annotated with Pfam domains

Pilot Study: Metabolic and microbial profiling of lung cancer
Wake Forest Baptist Comprehensive Cancer Center (WFBCCC)
WFBCCC # 03219

and GO terms, and the abundance of functional categories will be estimated to build a functional profile for each sample.

The results from the taxonomic and functional profiling will each be merged to estimate similarities and differences among the samples. Heat maps will be generated using Euclidean distance and clustering based on average linkage to assess functional similarities between samples, and principal component analysis (PCA) ordination of Bray-Curtis similarity between samples will be used to visualize the microbiota diversity across the samples.

Data Storage: All research data collected on this study will be stored on Wake Forest Baptist Medical Center password protected computers and servers.

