6.0 Analytic Plan

6.1 Sample Size and Power

This is a pilot study therefore; many of the objectives are exploratory in nature. With this in mind, we plan to recruit two cohorts of patients with this study, 45 female and 45 males. In order to be able to examine the questions concerning the possible relationships of metabolic and microbial signatures over time and with lung cancer outcomes, both pre- and post- surgery measures are needed. Therefore, each patient must provide both a pre- and post-surgery sample (optional blood will be allowed) in order to be used in the signature analyses. If a post collection is not performed or collection is unsatisfactory, the patient will be replaced. Therefore, our target sample size of 90 patients (45 male/45 female) is the target for patients with both pre- and post- samples collected.

Pilot Study: Metabolic and microbial profiling of lung cancer
Wake Forest Baptist Comprehensive Cancer Center (WFBCCC)
WFBCCC # 03219

First, for the primary objective of assessing feasibility, we can determine the total number of patients needed in order to enroll 90 patients. To examine this question we will determine 1) the number of patients screened for the trial, 2) among those screened, the number who are eligible, 3) among those eligible, the number who consent to participate, 4) among those who participate, the number who provide pre-surgery samples, and 5) among those who provide pre-surgery samples, the number who provide post-surgery samples. Based on our design we will enroll patients until 90 provide pre- and post- surgery samples.

Since we do not know prospectively how many patients will be needed to enroll 90 we will conservatively estimate several possible scenarios and for each scenario describe the width of the corresponding 95% Exact Clopper Pearson confidence interval for proportions.

The table below shows different total number of patients needed to enroll 90 for the study, beginning with 120 (75% enrollment rate) to 180 (50% enrollment rate).

# screened and eligible	Number enrolled	Enrollment rate	Lower 95% limit	Upper 95% limit
120	90	75%	0.66	0.82
150	90	60%	0.52	0.68
180	90	50%	0.42	0.58

As can be seen from the above, the confidence intervals for each scenario are approximately +/- 10% or less depending on the scenario observed.

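### Contaminant reads are removed by matching to a blank extraction, with no abundance, prevalence or batch rule, so low-biomass microbial profiles may keep contaminants

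*Combined protocol and SAP*

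**What the plan says.** Section 4.2.2 (Biofluid and tissue microbiome analysis) is the only text on sequencing contamination. It covers three sample types: "DNA will be extracted from each blood, saliva and lung tumor tissue sample". Libraries are levelled before pooling ("DNA libraries will be normalized and quantified prior to pooling to ensure equal library representation"), but the plan does not say whether the blank is levelled with them.

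The contamination rule is that "reads for each sample will be aligned to those in a blank extraction sample (negative control) that will be processed from DNA extraction". The plan then says how far the blank is carried and what it is for: "through library preparation to identify and remove contaminating sequences". What survives goes forward: "The filtered reads will then be aligned to a reference database consisting of complete genomes in the RefSeq database". The same filtered reads are then assembled for the functional profile.

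The plan gives no identity or overlap threshold and no comparison of amounts in blank and sample. It does not state the number of blanks per batch, or whether a patient's two visits share a batch.

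On numbers, section 6.1 says "our target sample size of 90 patients (45 male/45 female) is the target for patients with both pre- and post- samples collected", and for blood "optional blood will be allowed".

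**The concern.** Aligning sample reads to blank reads makes removal depend on how deeply the blank was sequenced and on which batch it came from. A contaminant is an organism, and all its reads should be treated alike. This filter treats them according to whether the blank happened to contain a matching fragment.

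The exposure is greatest in blood and tumour. These are expected to hold little microbial DNA (general knowledge, not stated in the plan), so a modest amount of reagent DNA can make up much of the profile.

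Section 6.3 takes pre/post change as the sign of association with lung cancer. Section 6.1 uses the resulting effect sizes, without multiplicity adjustment, to rank markers for future studies. A residual contaminant that tracks batch or DNA yield could be ranked as a candidate.

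**Working it through.** **1. The plan's own figure.** Section 6.1 gives 80% power for a 0.30 SD pre/post difference with 90 patients at two-sided alpha 0.05. For a paired t-test the noncentrality is 0.30 × √90 = 2.85 on 89 degrees of freedom, and power is 80.4%. The figure reproduces. It does not bear on contamination. The plan gives no figure for the filter, so steps 3 to 5 are bounding arithmetic on assumed inputs.

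**2. Extracts.** This counts the 90 patients with complete pairs, one extract per sample and a tumour sample from each.
- Without blood: 90 × (2 saliva + 1 tumour) = 270.
- With all blood: 90 × (2 + 1 + 2) = 450.

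No batch size is stated. If a batch held 96 extracts (assumption), this would be 270/96 = 2.8 to 450/96 = 4.7, so 3 to 5 batches.

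**3. Share of a contaminant's reads removed.** Assume blank reads fall at random on a genome of G bases, and treat reads singly (150 bases, two per pair, so N = 2 × pairs). If a sample read is removed when it overlaps a single blank read by at least m bases, the share removed is 1 − exp(−N × W / G), with W = 2 × (150 − m). Any overlap gives W ≈ 300. A 90% overlap (135 bases) gives W = 30. The share of genome bases covered uses W = 150. With G = 4 Mb (assumption):

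| Contaminant pairs in blank | Genome covered | Reads removed, 90% overlap | Reads removed, any overlap |
|---|---|---|---|
| 1,000 | 7% | 1% | 14% |
| 5,000 | 31% | 7% | 53% |
| 10,000 | 53% | 14% | 78% |
| 100,000 | >99% | 78% | >99% |

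For example, at 10,000 pairs with 90% overlap: 1 − exp(−20,000 × 30 / 4,000,000) = 1 − exp(−0.15) = 14%. The plan fixes neither the blank's depth nor the overlap rule.

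**4. Contaminants absent from the blank.** If a contaminant occurs in a share p of extractions, k independent blanks all miss it with probability (1 − p)^k.

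| p (assumed) | 1 blank | 5 blanks |
|---|---|---|
| 10% | 90% | 59% |
| 30% | 70% | 17% |
| 50% | 50% | 3% |
| 95% | 5% | <0.1% |

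One blank is adequate for contaminants present nearly everywhere, and poor for those confined to some batches.

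**5. Removal of true reads, if sample DNA reaches the blank.** Take 3,000 carried-over pairs from a 2 Mb species (assumption), so N = 6,000. Genome covered is 1 − exp(−0.45) = 36%. True reads removed are 1 − exp(−0.09) = 9% under the 90% rule and 1 − exp(−0.9) = 59% under any overlap. With only 100 single reads carried over, coverage is 1 − exp(−0.0075) = 0.7%. The effect runs from negligible to large.

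**6. Which analyses are exposed.** A taxon deleted alike at both visits is lost, and no change in it is created. False pre/post change needs residual contamination that differs between visits, through batch or DNA yield. The plan controls neither. The stage, pulmonary-function and cluster analyses in section 6.3 compare patients with each other, so within-patient pairing gives no protection there. Tumour is collected once (section 4.3), so it has no paired comparison at all.

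**The case against.** The strongest reply is that this is a missing laboratory detail in an exploratory part of a pilot. A blank, in the singular, may mean one per batch. The primary outcome is a set of feasibility proportions that sequencing does not touch. Section 6.1 presents marker results as a ranking for later studies. All of that stands and limits the reach.

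A reader might also infer several stronger things that the documents do not support:
- **That every matching read is deleted.** The text gives no rule for keeping a matching read, but it does not say this.
- **That oral DNA has leaked into the blank.** Nothing says or implies it; it is a possibility only.
- **That accrual of more than a year forces many batches.** Section 4.2.2 has biofluids frozen at −80 °C until analysis, so extraction need not follow the accrual calendar. The case for several batches rests on volume.
- **That genome coverage equals the share of reads removed.** Step 3 shows how far the two differ.
- **That the filter itself manufactures pre/post change.** Uniform deletion mainly loses signal.

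The reply does not dispose of the rule. One blank per batch would deal with batch-specific contaminants, but removal would still depend on which fragments each blank happened to sequence.

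**Conclusion.** The point holds as a weakness of method with limited reach, and it should be fixed before extraction starts. The plan states a read-matching rule whose effect depends on the blank's depth, an unstated match threshold and batch. On the plain reading, one blank serves 270 to 450 extracts of very different types. Blood and tumour profiles may keep contaminants, and true reads may be lost if there is carry-over.

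It would go too far to say that the profiles are distorted. The size cannot be computed, because the documents give no batch count, read depth, match rule or contamination rate. The illustrations above rest on assumed genome sizes, read counts and prevalences, and they span almost no effect to near-complete removal or near-certain failure. False pre/post change further requires that a patient's visits differ in batch or yield. The results at risk are the secondary microbial analyses.

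**What to change.** In section 4.2.2:

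- Carry at least one blank per extraction and library batch through sequencing, and state the number.
- Replace read subtraction with taxon-level contaminant calls, based on prevalence or abundance in blanks versus samples and made separately for saliva, blood and tumour.
- Do not rely on total DNA concentration for these calls in blood and tumour. The planned measurement ("The quantity and quality of the DNA extracts will be determined using a DeNovix DS-11 FX+ Spectrophotometer/Fluorometer") does not separate host from microbial DNA, and host DNA is likely to dominate there.
- Extract each patient's pre- and post-surgery samples in the same batch, which frozen storage allows.
- For functional profiles, remove reads assigned to flagged taxa before assembly. A taxon list cannot be applied directly to the Pfam and GO output, because the plan describes no taxonomic assignment of contigs.
- Report taxonomic results with and without filtering.

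The cost is a few extra blank libraries and one added read-assignment step. The downside is possible loss of genuine taxa that also occur in reagents, which the unfiltered results would show. Extraction blanks will still not reveal contamination that enters earlier, at sample collection or tumour banking.
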